### 3 Study design

This is an open-label, multi center, single arm study with flexible dosing allowing both dose adjustment and one drug holiday per patient.

The study design consists of 3 parts:

- Screening Epoch (0 2 weeks): required for all patients to assess initial eligibility.
- **Open-label Treatment Epoch (128 weeks):** Individual patients are treated for 128 weeks in the open-label treatment phase. During this open-label Treatment Epoch the erenumab dose may be adjusted from 70 mg to 140 mg or vice versa by discretion of the physician at any scheduled study visit. Additionally, a voluntary single treatment interruption ('drug holiday') of up to 24 weeks (approximately six months) may be introduced after at least 12 weeks of treatment in the open-label Treatment Epoch.
- Follow-up Epoch (4 weeks): A Follow-Up Visit 4 weeks after the last regular study visit (8 weeks after last IMP application) will be required as part of routine safety monitoring.

End of trial will occur when the last patient completes last visit (LPLV).

Figure 3-1	Study Design	
Screening Epoch Week -2 to Day -1	Open-label Treatment Epoch Day 1 to Week 128	Safety Follow-Up Epoch Week 128 to Week 132
	70 mg or 140 mg erenumab	
	optional drug	*

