#### 6.4 **Dose escalation and dose modification**

At study start, the subjects will be assigned to the latest administered dose of CAMG334ADE01 trial regardless of verum or placebo. Dose modification can be performed at the discretion of the physician at any of the following visits throughout the Open-label Treatment Epoch of the study according to the SmPC.

Dose modifications include dose escalation from 70 mg to 140 mg erenumab or dose reduction from 140 mg to 70 mg erenumab. One voluntary treatment interruption (drug holiday) per patient may be conducted but earliest after 12 weeks of treatment and for up to 24 weeks during the open-label treatment Epoch. Afterwards, patients may return to treatment.

There is no dose escalation guideline other than the SmPC. In clinical studies there was no clear dose-dependent safety signal combined with a comparable overall efficacy trend between 70 mg and 140 mg erenumab. Both 70 mg and 140 mg erenumab are considered to offer an optimal benefit-risk ratio for patients with some patients obtaining an additional benefit from the 140 mg dose.

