#### 6.6.2 Instruction for prescribing and taking study treatment

The investigational product dose is either 70 mg or 140 mg depending on the investigators decision, which has to be made for each patient individually and in accordance with the product information: the recommended dose is 70 mg, some patients may benefit from 140 mg (see Section 5.1 of AIMOVIG® SmpC).

In case of insufficient response, the dose may be escalated from 70 mg to 140 mg. Possible reasons for up-titration could be, but are not limited to:

- insufficient response as deemed by physician and/or patient
- reduction of acute medication use not satisfactory
- insufficient improvement in life quality

The dose may also be reduced from 140 mg to 70 mg. Possible reasons for down-titration could be, but are not limited to:

- complete response as deemed by physician and/or patient
- suspected treatment dependent adverse events

A dose adjustment can be performed at any scheduled study visit during the open-label Treatment Epoch.

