# 12.3 **Treatments**

The Safety set will be used for the analyses below. Categorical data will be summarized as frequencies and percentages. For continuous data, mean, standard deviation, median, 25th and 75th percentiles, minimum, and maximum will be presented.

A data listing and a summary of erenumab administered will be provided. Unless otherwise specified, patients assigned to 70 mg or 140 mg erenumab dose will be analyzed together under one treatment arm erenumab. The analysis by dose will be detailed in SAP as needed.

Concomitant medications and significant non-drug therapies prior to and after the start of the study treatment will be listed and summarized according to the Anatomical Therapeutic Chemical (ATC) classification system.

A data listing and summary of rescue medications will be provided.

The duration of exposure to erenumab will be summarized by means of descriptive statistics using the safety set. Concomitant medications and significant non-drug therapies prior to and after the start of the study treatment will be listed and summarized according to the Anatomical Therapeutic Chemical (ATC) classification system.

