#### 12.5.2 Safety endpoints

For all safety analyses, the safety set will be used. All listings and tables will be presented.

Safety summaries (tables, figures) include only data from the on-treatment period with the exception of baseline data which will also be summarized where appropriate (e.g. change from baseline summaries). In addition, a separate summary for death including on treatment and post treatment deaths will be provided. In particular, summary tables for adverse events (AEs) will summarize only on-treatment events, with a start date during the on-treatment period (treatment-emergent AEs).

The on-treatment period lasts from the date of first administration of study treatment to 112 days after the date of the last actual administration of study treatment.

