
Completion of drug holiday

Patients are defined to have completed their drug holiday if they either returned after drug holiday (see below) or if they discontinued study treatment, i.e. date of first dose after drug holiday or date of discontinuation of study treatment or date of study completion/discontinuation is given.

Drug holiday initiation period

The drug holiday initiation period

is defined as the 28 days-interval after start of the drug holiday

initiation period.

Start of drug holiday initiation period

The start date of drug holiday initiation period is defined as date of "planned date of last dose before drug holiday" from the eCRF + 1.

Novartis	Confidential	Page 10 of 34
SAP v1.1		CAMG334ADE03

Start of actual drug holiday period

The start date of the actual drug holiday period is defined as date of "planned date of last dose before drug holiday" + 28.

Patient-level End of Study (EoS) Date

The end of study (EoS) date for each subject is defined as the last date on which the subject participated in the study. The date will be recorded on the Treatment / study Completion eCRF page (Date of study completion/discontinuation).

On-treatment period

The on-treatment period lasts from the date of first administration of study treatment to 84 days after the date of the last actual administration of study treatment.

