2.4 Treatments (study treatment, rescue medication, concomitant therapies, compliance)

2.4.1 Study treatment / compliance

The analysis of study treatment data will be based on the SAF.

Novartis	Confidential	Page 16 of 34
SAP v1.1		CAMG334ADE03

A data listing and a summary of erenumab administered will be provided. The summary will include

- duration of exposure summarized descriptively, patients assigned to 70 mg or 140 mg erenumab dose will be analyzed together under one treatment arm erenumab
- number and percentage of patients with starting dose of 70 mg or 140 mg
- number and percentage of patients with dose reduction or dose increase and the corresponding reason

2.4.2 **Prior**, concomitant and post therapies

Prior and concomitant medication will be recorded on the 'Prior/concomitant medication/nondrug therapies' eCRF page. Ongoing medication from HER-MES will be recorded on the eCRF page 'Ongoing concomitant medication/non-drug therapies from HER-MES'. All concomitant medication from the HER-MES trial will be taken over as prior or concomitant medication.

The number and percentage of patients receiving rescue medications will be reported. The number and percentage of patients receiving concomitant medications and significant non-drug therapy will be summarized by ATC level 1 and preferred name (coded by WHO Anatomic Therapeutic Chemical classification [ATC]) and by treatment group.

The use of concomitant medications and significant non-drug therapy during the follow-up period will be summarized in the same way, in a separate table.

Data listings of rescue medications and concomitant medications and significant non-drug therapy will be provided.

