2.8.1 Adverse events (AEs)

In the frame of safety analysis the following treatment-emergent AE types will be considered:

- Any AE
- Study treatment related AE
- AE leading to study treatment discontinuation
- AE leading to dose adjustment (including study treatment discontinuation)
- Serious AE (SAE)
- Study treatment related SAE
- SAE leading to study treatment discontinuation
- Death

The Medical Dictionary for Regulatory Activities (MedDRA) version 24.1 or later will be used to code all adverse events (AE) to a system organ class (SOC) and a preferred term (PT).

Novartis	Confidential	Page 19 of 34
SAP v1.1		CAMG334ADE03

The SOCs will be presented in the alphabetic order and PTs will be ordered within the SOCs by decreasing order of frequency.

The number (and percentage) of subjects with treatment emergent adverse events (events started after the first dose of study medication or events present prior to start of treatment but increased in severity based on preferred term) will be summarized in the following ways:

- by primary system organ class and preferred term.
- by primary system organ class, preferred term and maximum severity
- by Standardized MedDRA Query (SMQ) and preferred term

If a patient reported more than one adverse event with the same PT, the adverse event with the greatest severity will be presented. If a patient reported more than one adverse event within the same primary system organ class, the patient will be counted only once with the greatest severity at the system organ class level, where applicable.

The overview of adverse events occurring during treatment will additionally be presented by starting dose (70mg/140mg).

All AEs, deaths (see see section 2.8.2 Deaths for details), SAEs and AEs leading to permanent study drug discontinuation will be listed separately.

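### Does tabulating adverse events by starting dose misstate safety by dose, given that the dose can change at any scheduled visit?

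*SAP*

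**What the plan says.** Protocol section 3 provides that "the erenumab dose may be adjusted from 70 mg to 140 mg or vice versa by discretion of the physician at any scheduled study visit". Section 6.4 confirms that changes go both ways: "Dose modifications include dose escalation from 70 mg to 140 mg erenumab or dose reduction from 140 mg to 70 mg erenumab". Section 6.6.2 lists insufficient response among the reasons for going up, and complete response and "suspected treatment dependent adverse events" among the reasons for going down. One drug holiday of up to 24 weeks is also allowed.

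On analysis, protocol 12.3 pools the two doses as one erenumab arm unless otherwise specified and adds: "The analysis by dose will be detailed in SAP as needed". The SAP's readable answer for adverse events is in 2.8.1: "The overview of adverse events occurring during treatment will additionally be presented by starting dose (70mg/140mg"). SAP 2.4.1 also reports the number starting on each dose and the "number and percentage of patients with dose reduction or dose increase and the corresponding reason". SAP 2.1.1.4 and 2.8.1 define and report events that led to a dose increase, reduction, interruption or withdrawal. The primary endpoint (SAP 2.5) is one pooled rate, and its subgroups in 2.5.4 do not include dose.

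**The concern.** The primary objective names both 70 mg and 140 mg, and a reader will see the two starting-dose columns side by side. Starting dose describes a patient's entry to a 128-week epoch, not exposure through it. The on-treatment period runs from first dose to a fixed time after the last one, so it includes any holiday after which dosing resumed. An event after a switch or in a holiday therefore counts under a dose the patient may not be receiving at that time.

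If patients switch permanently, the rate ratio is constant and the starting groups are otherwise alike, any contrast between the columns is pulled toward no difference. A real difference between doses could then be understated. The table also cannot show whether an event began on 70 mg, on 140 mg or off treatment.

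**Working it through.** **What each output needs from dose**

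- Primary rate (SAP 2.5): pooled over dose, so unchanged by any dose grouping.
- Secondary endpoints (SAP 2.6): proportions discontinuing, pooled over dose, so also unchanged.
- Overview by starting dose (SAP 2.8.1): counts patients by a characteristic fixed before any event in this study. The label matches the content.

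**Possible dilution**

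The documents give no switching rate. The illustration assumes that a share p of 70 mg starters moves to 140 mg for good at week t, that 140 mg starters stay on 140 mg, and that everyone is followed for 128 weeks without a holiday.

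Share of 70 mg starters' person-time on 140 mg: f = p(128 − t)/128.

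- p = 0.1, t = 60: f = 0.1 × 68/128 = 0.053
- p = 0.5, t = 12: f = 0.5 × 116/128 = 0.453

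Ratio shown by starting dose for a true ratio RR: RR/(1 − f + f·RR).

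| True RR | f = 0.053 | f = 0.453 |
|---|---|---|
| 1.1 | 1.1/1.0053 = 1.094 | 1.1/1.0453 = 1.052 |
| 1.5 | 1.5/1.0266 = 1.461 | 1.5/1.2266 = 1.223 |

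The overview counts subjects, so the percent scale is closer to what it will show. Take 85% with any event on constant 70 mg (a row of the protocol's precision table in 12.8.1) and a constant hazard h = −ln(0.15)/128 per week. With RR = 1.1:

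- Constant 140 mg: 1 − 0.15^1.1 = 87.59%, a true gap of 2.59 points.
- 70 mg starters: (1 − p) × 85% + p × {1 − exp[−h(t + 1.1(128 − t))]} = 85.14% for p = 0.1, t = 60, and 86.18% for p = 0.5, t = 12.
- Gap shown: 87.59 − 85.14 = 2.45 points and 87.59 − 86.18 = 1.41 points. The loss is 0.14 to 1.18 points.

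**Sampling error for comparison**

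With an assumed even split of the protocol's 500 patients, the 95% half-width of a difference at 85% is 1.96 × √(2 × 0.85 × 0.15/250) = 6.3 points. The whole true gap of 2.59 points is less than half of that. So even if switching in both directions removed the gap entirely, the change would stay within sampling error.

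At RR = 1.5 the picture differs. Constant 140 mg gives 1 − 0.15^1.5 = 94.19%, a gap of 9.19 points. At p = 0.5, t = 12 the 70 mg starters show 89.33%, so the gap falls to 4.87 points (unrounded). Dilution of that size would matter to someone using the table as a dose comparison. Protocol 4.3, however, reports a similar safety profile for the two doses.

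**Would dose at onset be cleaner?**

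- Suspected adverse events are a listed reason to leave 140 mg, so patients prone to events can drop out of the 140 mg row.
- Insufficient response is a listed reason to go up, and 140 mg time gained that way falls later in the study.
- A holiday row is not cleanly off drug. SAP 2.1.1.1 starts the actual holiday 28 days after the last planned dose. Taking the SAP's 84-day tail as a proxy for carry-over, (84 − 28)/168 = 33% of a full 24-week holiday lies inside it. With the protocol's 112-day tail, (112 − 28)/168 = 50% does.

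**The case for a change.** The strongest case for the extra table is that starting dose is carried over from the parent trial whether the patient received active drug or placebo, so it says little about long exposure. Protocol 4.1 also says the effect of a treatment interruption on safety will be investigated, and a full holiday is 24/128 = 19% of the epoch. Event dates, dosing records and holiday dates are all collected, so a descriptive table of rates by dose at onset needs no new data.

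These facts stand, and such a table would show something the overview cannot. They do not make the plan wrong. The protocol leaves analysis by dose to the SAP's judgement. The holiday question may be answered in SAP text that is not available: a Drug Holiday Analysis Set is defined in 2.2, the section numbering has gaps, and the table shells are a separate document. The absence of a holiday or dose-at-onset table from the readable text is therefore not evidence that none is planned.

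The dilution argument is also less firm than it looks. Starting dose is not randomised, so selection could move the contrast either way.

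One related discrepancy is real but separate. The on-treatment period ends "112 days after the date of the last actual administration of study treatment" in protocol 12.5.2 and "84 days after the date of the last actual administration of study treatment" in SAP 2.1.1.1. Those two passages need to be reconciled, but the conflict bears on every safety summary and does not come from grouping by starting dose.

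**Conclusion.** The concern does not hold. Grouping by starting dose is correctly labelled, fixed before any event in this study and within the discretion the protocol gives the SAP. It touches neither the primary rate nor the secondary proportions. At a rate ratio of 1.1, the modelled dilution is at most 1.2 points on the percent-of-subjects scale, against a half-width of 6.3 points. That rests on assumed switching of 10% to 50% between weeks 12 and 60, full follow-up, a constant hazard and an even split of 500 patients. The dilution would be material only if the doses differed substantially in safety, which the protocol's own summary does not suggest, and only if the overview were read as a dose comparison, which no objective calls for. A table by dose at onset would exchange this dilution for confounding by response, by adverse events and by time on study. Statisticians could reasonably choose either, so the choice made here is a trade-off and not a defect.

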2.8.1.1 Adverse events of special interest / grouping of AEs

Not applicable

2.8.2 Deaths

Deaths will be listed including the start date of the study treatment, the last date on study treatment, the death date and the reason for death.

2.8.3 Laboratory data

Summary statistics of laboratory hematology and blood chemistry results will be presented as absolute values as well as change from baseline by visit and laboratory test category. Change from baseline will be summarized for each time point and only for patients with both, baseline and post-baseline assessment. Shift tables will be used to compare baseline to the worst on-treatment value.

All laboratory data with clinically notable values will be listed by subject and visit. Abnormal values will be marked according to the definitions of the central laboratory (see section 5.8 Abnormal laboratory value definitions).

2.8.4 Other safety data

2.8.4.1 12-lead ECG

For the numeric ECG measurements

• ECG Mean Heart Rate

- PR Interval
- QRS Duration
- QT Interval
- QTcF Interval
- RR Interval

summary statistics will be presented by visit. Descriptive summary statistics for the change from baseline will be calculated for patients with available ECG data at both time points.

All ECG data will be listed by subject and visit.

